15.2 N/A

16.0 Vulnerable Populations

16.1 N/A

17.0 Community-Based Participatory Research

17.1 N/A

18.0 Sharing of Results with Subjects

18.1 N/A

19.0 Setting

19.1 Our research team will identify and recruit potential subjects from people who are local to Shreveport, LA and local clinical/academic settings.

- Potential subjects will be recruited via word of mouth on the campus of LSUHS and those in the community of Shreveport, LA and the surrounding areas.
- Research procedures will be performed at the SHPS at LSUHS main campus in Shreveport, LA. The rehabilitation clinic will be used to gather anthropometric measurements and the motion analysis lab, room 2-217, will be utilized for sEMG placement and FSDT. A separate conference room will be used to assign and educate participants on their HEP in order to preserve blinding of the data analyst.
- There will not be composition and involvement of any community advisory board. There will not be any research conducted outside of the organization and its affiliates.

20.0 Resources Available

20.1 The three student investigators (GD, DB, and MM) are DPT students in the SHSP at LSUHS. They will be educated on the procedures of the FDST (reference numbers), sEMG electrode placement, and data collection and interpretation (reference number) by primary investigator (EM), who is a board-certified orthopedic physical therapist with 9 years of experience and the co-investigator (DF), who is a board-certified orthopedic physical therapist with 13 years of experience. The primary investigator (EM) and co-investigator (DF) have also conducted similar studies previously that used the FDST and sEMG data. The primary investigator (EM) and co-investigator (DF) will assist the student investigators as needed throughout the study. Multiple training sessions will occur prior to starting data collection to ensure student investigators are reliably able to place sEMG on the targeted muscles.

20.2 In local clinical/academic settings, the total number of first- and second-year DPT students currently enrolled in the SHPS at LSUHS is 70. The total number of first- and second-year DOT students enrolled in the SHSP is 52.

The total number of medical students in the first- and second-year class is 300. Given the required N = 38, there are enough potential subjects in local clinical/academic settings to successfully complete the study.

- Currently, student investigators are enrolled in independent study for the Fall 2025 semester to receive IRB approval. The month of January 2026 will be for recruitment of subjects. Data collection will begin in spring of 2026 and will conclude by May 2026. The investigators will be enrolled in a 2-credit research course during this semester to allow time to conduct the research and work on presenting the research. The investigators, EM and DF, will each provide 5% FTE, which is within their scholarship FTE distribution considering other research commitments. During the Summer 2026 semester, the student investigators will begin analyzing the data and dissemination of data. All data analysis will be concluded by August 2026.
- The rehabilitation clinic in SHSP at LSUHS, located on the ground floor, has scales to measure weight and vertical ruler to measure height, and other anthropometric data. The motion analysis lab, room 2-217 in SHSP at LSUHS has a treatment mat, sEMG materials and technology, and an open area to analyze movement.
- Our study has less than minimal risk, thus no medical or psychological resources should be needed due to there being no anticipated consequences of human research.
- The PI will complete the DOA, including the assigning of roles and responsibilities, and educate each investigator at the time of signing.

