Table of Events	# of times test or procedure will be performed
Written informed consent	1
Anthropometric assessment (height, weight, BMI, sex, age, leg dominance)	1
FSDT	3
sEMG	2
HEP Education	1
Compliance Chart Education	1
HEP Midpoint Check in	1
HEP	16
Compliance chart document	16

9.4 To reduce the risk of confidentiality, participants will be assigned identification numbers. All hardcopy data including group assignments will be stored in the PI's office in a locked drawer. All electronic data will be stored using OneDrive connected to school email addresses with a password. The investigator performing the data analysis will be blinded.

An informed consent document with participant identification numbers will be used to obtain consent from the participants. An identification number will be assigned to the name of each participant along with their group assignment. An identification number key will be used to maintain confidentiality when performing data collection and analysis, which will be stored on the PI's password protected computer. Only study members will have access to this document.

A sign-up sheet for the data collection days will be created that will allow participants to sign up with their assigned identification number. Investigators will use an excel sheet to collect data (see data collection form as part of submission). Participants will track their HEP performance on the compliance chart that will be provided to each participant. A paper copy of the HEP with pictures, written instructions, and a QR code for video instructions will be given to the participants.

To reduce the risk of muscle soreness, participants will be educated on appropriate exercise performance and to space the sessions at least two days apart. Once all hip activation exercises can be completed for one minute on the dominant LE without a break, participants will be educated to add the yellow TheraBand. Once the exercises can be completed for one minute with the yellow TheraBand on the dominant LE without a break, participants will be educated on progressing to the red TheraBand that has a higher resistance.

To reduce the privacy risk of participants being recorded on video for data collection and the possibility of the video recording being lost or exposed, all electronic data will be stored using Sharepoint connected to school email

addresses with a password. This information will also be kept private by utilizing the assigned participant identification numbers.

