- 11.3 To reduce the risk of loss of confidentiality, participants will be assigned ID numbers on their informed consent form. All hardcopy data will be stored in a locked drawer in room 2-236 in the SHPS at LSUHS. All electronic data will be stored using Sharepoint/OneDrive connected to school email addresses with a password. The investigator performing the data analysis will be blinded. Participants will be identified by their ID number throughout the study, and group assignment will be recorded by ID number. A sign-up sheet for data collection times will also use ID number. Throughout the study, data will be recorded by ID number on the data collection sheet attached to this submission. For the participants to track their home exercise sessions, a compliance chart will be created for them again with only ID number attached to the compliance chart.

- 11.4 The student investigators (DB, GD, MM) will be educated on the proper procedures of the FSDT, sEMG data collection, and the HEP by the primary investigator (EM) and co-investigator (DF). The FSDT will be analyzed by the three student investigators (DB, GD, MM). The student investigators (DB, GD, MM) will record and average their scores for the FSDT following the completion of five repetitions to improve the quality of the data. (Super script). The sEMG electrodes will be placed on the female participants by GD. MM will explain the FSDT procedure to every participant. DB, GD, MM will explain the hipactivation exercises on the HEP and will explain the movement retraining program HEP and the QR code access for videos. DB, GD, and MM will explain the compliance chart to the participants. The primary investigator (EM) is a board-certified orthopedic physical therapist with 8 years of experience, who has published research on this test. (super script) The co-investigator? (DF) is also a board-certified orthopedic physical therapist with 13 years of experience, who also has published research on this test with the primary investigator.

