- 11.5 The data that will be collected during the study includesheight, weight, BMI, sex, leg dominance, MVIC of each muscle group, FSDT pre and post HEP, recorded FSDT video, sEMG from gluteus medius and maximus on the dominant leg during FSDT pre and post HEP, and HEP compliance. Data storage will follow the guidelines in section 9.4. The data will be stored for the duration of the study and throughout the following semester while analyzing and finalizing data for presentation. The data will only be

kept up to one year after the completion of the data analysis in the event that the research wants to be continued. The only people who will have access to this information will be the primary investigator and student investigators (EM, DB, GD, MM) since the co-investigator (DF) that is doing the data analysis will be blinded. The primary investigator and student investigators are responsible for the receipt and transmission of the data. The student investigators (DB, GM, MM) are responsible for data processing. Data will be manually transported to EM office room 2-236 in the SAHP at LSUHS. Electronic data will remain on Sharepoint.

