24.0 Provisions to Protect the Privacy Interests of Subjects

24.1 All individuals participating in the study will be given an identification number to protect their personal identity and to maintain single-blind confidentiality. Participants will only be expected to interact with the investigators (EM, DF, GD, DB, MM) during the study. Participants will only be expected to provide personal information to the primary investigators (EM, DF) and student investigators (GD, DB, MM).

24.2 Only the investigators (EM, GD, DB, MM) will be in the room during data collection, and any questions will be asked individually with the investigators. If another participant is in the room learning the HEP, the view will be obstructed with a divider to ensure confidentiality. The co-investigator (DF) will be asked to leave the room during HEP demonstration to each participant to maintain confidentiality. Each participant will be asked not to discuss their HEP when co-investigator (DF) is in the room to maintain confidentiality. Any written data will refer to participants with numbers, not actual names. No previous medical history or identifying information will be entered into the data collection.

24.3 Any information about the subjects will be verbally reported to the investigator, except for information regarding their HEP which will not be reported to the co-investigator (DF). Recorded data will be placed on a master data sheet and will be shared between investigators on Sharepoint/OneDrive. Individuals not involved in the investigation will not have access to the data.

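### The plan promises a blinded data analyst, but its sections on who analyses, who has access and who processes the sEMG do not secure that

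*Combined protocol and SAP*

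**What the plan says.** Blinding of the analyst is a deliberate feature of the plan. Section 9.4 states: "The investigator performing the data analysis will be blinded", and 11.3 repeats it. Section 11.5 identifies the co-investigator as the person "that is doing the data analysis will be blinded". Section 19.1 sets aside a separate room for assignment and teaching "in order to preserve blinding of the data analyst", and 24.2 has the co-investigator leave while exercises are demonstrated.

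Other sections pull against this:

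- **20.2** says "the student investigators will begin analyzing the data and dissemination of data".
- **11.4** says "The FSDT will be analyzed by the three student investigators".
- **11.5**, after listing the data to be collected, says "The only people who will have access to this information will be the primary investigator and student investigators". It also makes the students responsible for data processing.
- **24.3** says "Recorded data will be placed on a master data sheet and will be shared between investigators on Sharepoint/OneDrive".
- **11.3** says "group assignment will be recorded by ID number", and 9.4 leaves the identification key open to study members in general.

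**The concern.** In a trial where participants and teachers necessarily know the programme, a blinded analyst is one of the few protections against bias still available. It works only if three things are settled: one person does the analysis, that person receives the outcomes without a readable arm label, and anyone who prepares the data using judgement is masked as well. The protocol leaves each of these unclear or contradictory. If it is followed as written, the trial report could not safely state that the analysis was blinded. This is separate from the question of who rates the FSDT.

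**Working it through.** No arithmetic applies, because the point depends on no sample size, effect size or error rate. The check sets the sections side by side.

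1. **Who analyses?** Sections 9.4 and 11.3 promise a blinded analyst, and 11.5 says it is the co-investigator. Section 20.2 gives the start of analysis to the students. Section 11.4 also uses the word for the students' work on the FSDT, but the context there is scoring, so it is weaker evidence. No section reconciles 20.2 with 11.5.

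2. **Do the students know the arm?** Under 9.2 each participant is taught by one of three students, and 11.4 has the same three explaining both the hip-activation exercises and the movement retraining. The two programmes are visibly different. Each student therefore knows the arm of those he or she teaches, and collectively the students know all arms. The documents do not show that every student knows every allocation.

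3. **Can the named analyst obtain the data?** The list in 11.5 covers body measurements, leg dominance, MVIC, FSDT before and after, video, sEMG and compliance. Group assignment is not on it. Access to that list is confined to the primary investigator and students, with the co-investigator's blinding given as the reason. Taken literally, the sentence withholds the outcomes from the analyst and does not mention the allocation. Section 24.3 then shares the recorded data among investigators, and 24.1 counts the co-investigator as one. The two access rules cannot both hold.

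4. **Is the allocation closed to the analyst?** Section 11.3 stores group by ID. Section 9.4 describes an ID assigned to each name together with the group, and a key on the primary investigator's password-protected computer that study members may see. The co-investigator is a study member and is not excluded. The exception in 24.3 for exercise-programme information is attached to what is reported verbally; it does not say what the sheet or the key contains.

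5. **Does processing leave room for judgement?** Section 11.1 fixes a 10-500 Hz filter, rectification, 50 ms RMS smoothing, normalisation to MVIC and averaging over 5 repetitions. It treats each repetition as a separate trial but gives no rule for its onset or offset. The mean depends on that window, and the peak can. Section 11.5 gives this processing to the students, and no section masks the files.

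6. **Does analysis leave room for judgement?** For FSDT score and sEMG, 11.1 fixes the 2x2 repeated measures ANOVA, alpha of .05 and Tukey's HSD. It names no method for movement category (SA2) or dose response (SA5), so those choices would fall to whoever carries out the analysis.

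**The case against.** The strongest reply is that the intention is plain and the faults are loose drafting. Section 11.5 separates student processing from co-investigator analysis, and 20.2 is a semester timetable in a resources section, so its wording may mean processing. The access sentence in 11.5 gives blinding as its own reason, so it was probably meant to cover identifying or allocation data. Real safeguards exist: the separate room (19.1), the co-investigator leaving during demonstrations and participants being asked not to discuss their programme in that person's presence (24.2), the verbal-report exception (24.3), and hardcopy group assignments locked in the primary investigator's office (9.4). Section 20.2 also says that roles will be assigned in a delegation document.

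Much of this stands as a reading of intent. But no section says that 20.2 means processing only or that 11.5 means allocation only, and the delegation document is not part of the plan. Nor does the reply address unmasked sEMG processing or the open key.

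A reader might also infer more than the documents support:

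- **That the shared sheet unblinds the analyst.** Its columns are not described, and nothing says that it carries group.
- **That the 0/1 labels in 9.2 reveal the arm in the dataset.** They are described as allocation codes for the envelopes; no section says that they enter the analysis file.
- **That people who know the arm would choose the post hoc test.** Section 11.1 already fixes Tukey's HSD.
- **That the number of recordings processed measures the bias.** It would show how much material is exposed, not how far any result moves.

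**Conclusion.** The point holds as an internal inconsistency with a consequence for bias control. The plan states that the analyst is blinded, but its text does not secure this: two sections differ on who analyses, two differ on who may see the data, the key is not closed to the analyst, and a judgement-dependent sEMG step is done unmasked by people who teach the programmes. It should be corrected before sEMG processing and analysis begin.

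The documents do not show that blinding has failed or will fail, and neither the size nor the direction of any bias can be computed from them. The conclusion rests on reading 11.5, 20.2 and 24.3 as written, and on the absence of any masking step or repetition-window rule elsewhere in the text.

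**What to change.** - **Reconcile 11.5, 20.2 and 24.3.** State that the co-investigator is the sole analyst of the between-group comparisons and that students are limited to data entry and processing. Correct the access sentence in 11.5 so that the analyst can receive the outcome data.
- **Mask the sEMG.** Have the primary investigator relabel the files so that students process them without ID, arm or visit label. Each session's MVIC and FSDT recordings need a common scrambled code, because 11.1 normalises one to the other.
- **Close the allocation.** Exclude the analyst by role from the ID and allocation key in 9.4, and keep group and exercise-programme content off any sheet the analyst can open.
- **Supply a neutral analysis file.** After data freeze, the primary investigator provides a de-identified file with arms coded A and B. It should include a plain count of completed sessions, without exercise content, because SA5 cannot be analysed without adherence. The planned comparisons are completed before the code is opened.

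The cost is rewording plus relabelling and recoding by the primary investigator. A few hours is a working estimate, not a figure from the documents. No extra staff or visits are needed.

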21.0 Prior Approvals

- 21.1 Approval for the project will be obtained from the SHPS Associate Dean of Business, Technology and Research.

22.0 Recruitment Methods (Local)

- 22.1 Potential subjects will be recruited via word of mouth from people who are local to Shreveport, LA and local clinical/academic settings. Investigators (DF, GD, DB, and MM) will recruit students on the campus of LSUHS by going to different classrooms and informing potential participants about the study. A meeting will be held for all potential participants to obtain informed consent. Then, once informed consent has been obtained, the potential participants will complete a self-reported health questionnaire (PAR-Q) and a preliminary FSDT. If a potential participant cannot be present at this meeting, a meeting will be scheduled with the investigators to obtain informed consent and then the other measures.
- 22.2 The subjects will be recruited via word of mouth from people who are local to Shreveport, LA and local clinical/academic settings. Participants will be considered for participation if they meet all inclusion and exclusion criteria.
- 22.3 Potential subjects will first be identified via word of mouth through informing students on the campus of LSUHS about the study.

22.4 N/A

22.5 N/A

23.0 Local Number of Subjects

23.1 At least 38 subjects will be accrued locally

23.2 We plan to enroll 38 participants.

24.0 Provisions to Protect the Privacy Interests of Subjects

24.1 All individuals participating in the study will be given an identification number to protect their personal identity and to maintain single-blind confidentiality. Participants will only be expected to interact with the investigators (EM, DF, GD, DB, MM) during the study. Participants will only be expected to provide personal information to the primary investigators (EM, DF) and student investigators (GD, DB, MM).

24.2 Only the investigators (EM, GD, DB, MM) will be in the room during data collection, and any questions will be asked individually with the investigators. If another participant is in the room learning the HEP, the view will be obstructed with a divider to ensure confidentiality. The co-investigator (DF) will be asked to leave the room during HEP demonstration to each participant to maintain confidentiality. Each participant will be asked not to discuss their HEP when co-investigator (DF) is in the room to maintain confidentiality. Any written data will refer to participants with numbers, not actual names. No previous medical history or identifying information will be entered into the data collection.

24.3 Any information about the subjects will be verbally reported to the investigator, except for information regarding their HEP which will not be reported to the co-investigator (DF). Recorded data will be placed on a master data sheet and will be shared between investigators on Sharepoint/OneDrive. Individuals not involved in the investigation will not have access to the data.

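### Apart from a visual divider and individual questions, section 24.2 has no measure against the home exercise programme passing between arms, so the between-arm difference could be diluted

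*Combined protocol and SAP*

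**What the plan says.** All references are to the combined protocol and SAP.

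- **Teaching, section 24.2.** A second learner may be present: "If another participant is in the room learning the HEP, the view will be obstructed with a divider to ensure confidentiality". The same section says that "any questions will be asked individually with the investigators". The co-investigator, who analyses the data blinded, leaves during demonstrations.
- **Discussion, section 24.2.** "Each participant will be asked not to discuss their HEP when co-investigator" is in the room. The text supplied contains no other request of this kind.
- **Teaching room, section 19.1.** "A separate conference room will be used to assign and educate participants on their HEP in order to preserve blinding of the data analyst".
- **Source of participants.** Section 22.1 describes recruiting students on campus by "going to different classrooms and informing potential participants about the study", followed by a joint meeting for consent and screening. Section 20.2 says that "the total number of first- and second-year DPT students currently enrolled in the SHPS at LSUHS is 70", and adds 52 DOT and 300 medical students. Section 19.1 also allows recruitment from the surrounding community.
- **Contrast between arms, section 9.2.** Both arms receive the gluteal activation programme. Only the experimental arm also receives the movement retraining programme: single-leg Romanian deadlift, single-leg squat and split squat, with feedback cues.
- **Materials, sections 9.2 and 9.4.** Participants take home printed HEP instructions with a QR code to videos, and a chart for logging each HEP session. Exercise is at home, twice a week for eight weeks, with a form check after week 4.
- **Sample size, section 11.2.** N = 26 for the interaction in a 2x2 repeated measures ANOVA, raised to 38 for attrition and screening failures. Contamination is not mentioned.

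**The concern.** The planned difference between arms is three exercises with cues. Section 11.4 has the investigators explain both programmes aloud, and a divider does not stop sound, so a control participant being taught at the same time could hear the experimental programme described. The non-discussion request is not in force at that moment, because the co-investigator has left. It also does not cover the eight weeks between visits, when classmates in opposite arms may meet and each has a handout that is easy to show.

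A control who takes up the added exercises gains some of the experimental effect, and the FSDT and sEMG differences shrink. Nothing in the text supplied plans to record exercise done outside the assigned HEP. If the trial finds no difference, the team would therefore have no data with which to judge whether dilution contributed.

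**Working it through.** **Inputs.** From section 11.2: d = 0.58, two-sided alpha 0.05, target power 0.80 (printed there as beta), group-by-time interaction with two groups and two measurements, 20% attrition plus 10% screening failures. From section 9.2: equal allocation within strata. Assumed, because the documents give no value: pre-post correlation rho, and the share c of controls who gain the full added benefit.

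**Step 1: reproduce the plan's N.** Use the noncentral F test for the interaction, with f = d/2 = 0.29, m = 2 measurements, df = (1, N − 2), and

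lambda = f² × N × m / (1 − rho).

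At rho = 0.5 and N = 26: lambda = 0.0841 × 26 × 2 / 0.5 = 8.75, and power is 81.0%. N = 24 gives 77.5%, so 26 is the smallest even N that reaches 80%. The plan's figure reproduces.

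The choice of rho matters. The required N would be 36 at rho = 0.3 and 18 at rho = 0.7, and power at N = 26 would be 67.0% and 95.6%. The value 0.5 is used below because it returns the plan's 26.

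**Step 2: reproduce 38.** 26 / (1 − 0.30) = 37.1, which rounds up to 38 in equal arms. If all 38 are enrolled after screening and only attrition applies, 38 × 0.80 = 30.4, so about 30 are evaluable. Both 26 and 30 are carried forward.

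**Step 3: dilute the effect.** If a share c of controls gains the whole added benefit and the SD is unchanged, the expected difference becomes d' = 0.58 × (1 − c) and f' = 0.29 × (1 − c). For c = 10%: d' = 0.522, f' = 0.261, and at N = 26 lambda = 0.0681 × 26 × 4 = 7.08.

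| Controls contaminated (c) | d' | Power, N = 26 | Power, N = 30 |
|---|---|---|---|
| 0% | 0.580 | 81.0% | 86.6% |
| 5% | 0.551 | 76.9% | 83.0% |
| 10% | 0.522 | 72.4% | 78.8% |
| 20% | 0.464 | 62.2% | 68.9% |
| 30% | 0.406 | 51.1% | 57.4% |

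**Step 4: put c in persons.** With 26 evaluable there are 13 controls, so one full adopter is 1/13 = 7.7%. With 30 there are 15 controls, and one is 1/15 = 6.7%. The 5% and 10% rows therefore bracket a single control participant.

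**Step 5: partial adoption.** If adopters gain only a fraction g of the benefit, replace c by c × g. Ten percent of controls gaining half the benefit (0.10 × 0.5 = 0.05) falls on the 5% row.

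**Step 6: direction.** If the added programme has no effect, adopting it changes nothing in the control arm. The false-positive rate is not raised.

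**The case against.** The case on the other side has weight.

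- **Some safeguards exist.** A reader might infer that the measures protect only the co-investigator's blind. That goes too far: the divider keeps participants from seeing each other's programme and questions are individual, although the stated purpose is privacy. Section 24.1 also expects participants to deal only with the investigators, but that is an expectation and not an instruction to them.
- **Silence is not permission.** The documents do not allow participants to talk to each other about the HEP; they do not restrict it. The consent form, the HEP handout and the chart are not in the text supplied, and any of them may carry a non-sharing instruction. This stands, and they should be checked first.
- **Sections 19.1 and 24.2 need not conflict.** A room separate from the testing lab can still hold two learners and a divider.
- **The pool is wider than one class.** It is 70 + 52 + 300 = 422 students plus community members, and 38 is 9% of 422. That lowers the chance of contact but does not remove it, because recruitment goes classroom by classroom and by word of mouth.
- **Some tempting details are not in the documents.** They do not say that anyone can open the QR link, that the arms share a link, or that the added exercises need only what a control already has; section 2.3 makes a mirror part of the feedback. A misclassified dose in SA5 is also an inference: that aim concerns adherence to the HEP, and extra exercises do not alter the count of assigned sessions.
- **Full adoption is an extreme assumption.** Overhearing one explanation is far from eight weeks of cued practice. This stands, and the table shows sensitivity and is not a forecast.

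**Conclusion.** The point holds as a gap in section 24.2. Beyond a visual divider and individual questions, the section does not limit passage of the HEP between arms: a second participant may be in the room, presumably within hearing, during teaching, and the non-discussion request is tied to the co-investigator's presence. Shared classes and portable materials make the route plausible.

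The consequence is loss of power. At the plan's 26 evaluable there is only about one percentage point to spare, so 5% of controls fully adopting takes power from 81% to 77%, and 10% takes it to 72%. At 30 evaluable the figures are 87%, 83% and 79%. These rest on d = 0.58, an assumed correlation of 0.5, an unchanged SD, and full adoption with equal effect. No contamination rate is given, and partial adoption would cost less. The documents do not support a statement that contamination will occur or how much. The reason to act is that narrowing the route costs very little.

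**What to change.** 1. **Section 24.2, teaching.** Replace the divider sentence with a rule that HEP teaching and the week-4 form check are done with one participant at a time, in the separate room named in section 19.1.
2. **Section 24.2, discussion.** Extend the request, for example: *do not discuss or share your HEP, handout or QR code with any other participant until all post-testing is complete.* Check the consent form and handout first, and make them agree.
3. **Final visit only.** After the FSDT and sEMG have been recorded, ask each participant whether they did lower-limb exercises outside the assigned HEP. Report the answers by arm and keep everyone in the randomised comparison. The person asking should neither score the FSDT nor be the blinded analyst. Section 11.1 names one FSDT rater, whereas section 11.4 has all three student investigators scoring. If 11.4 governs, only the primary investigator is free for this, so settle that point when assigning the task.
4. **Week 4.** Do not name the experimental exercises to controls. Doing so halfway through would disclose the programme that the other measures are meant to keep apart.

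The cost is protocol wording, wider spacing of appointments for about 38 teaching sessions and the week-4 checks, and one question at an existing visit. The downside is slightly longer scheduling. The wording is most useful if it is in place before enrolment.
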